9.5 Exclusion criteria

Subjects must not enter the study if any of the following exclusion criteria are fulfilled:

1. History of any clinically significant disease or disorder which, in the opinion of the Investigator, may either put the subject at risk because of participation in the study, or influence the results or the subject's ability to participate in the study.
2. Any clinically significant illness, medical/surgical procedure or trauma within 4 weeks of the first use of IP.
3. Any planned major surgery within the duration of the study.
4. Any positive result on screening for serum hepatitis B surface antigen, hepatitis C antibody and Human Immunodeficiency Virus (HIV).
5. After 10 minutes supine rest at the time of screening, any vital signs values outside the following ranges:
 - Systolic blood pressure <90 or >140 mmHg, or
 - Diastolic blood pressure <50 or >90 mmHg, or
 - Pulse <40 or >90 bpm
6. Female subjects who are pregnant or who are currently breast feeding.
7. History of severe allergy/hypersensitivity or ongoing allergy/hypersensitivity, as judged by the Investigator, or history of hypersensitivity to drugs with a similar chemical structure or class to nicotine.
8. Planned treatment or treatment with another IP within 1 month or investigational drug within 3 months prior to Day -1. Subjects consented and screened but not dosed in previous phase I studies are not excluded.
9. Positive screen for drugs of abuse or alcohol at screening or on admission to the research unit prior to use of the IP.
10. History of alcohol abuse or excessive intake of alcohol, as judged by the Investigator.
11. Presence or history of drug abuse, as judged by the Investigator.
12. History of, or current use of, anabolic steroids, as judged by the Investigator.
13. Excessive caffeine consumption defined by a daily intake of >5 cups of caffeine containing beverages.
14. Plasma donation within one month of screening or blood donation (or corresponding blood loss) during the three months prior to screening.
15. Subjects who intend to change their smoking habit or make a quit attempt within the next 3 months from the screening visit.
16. Investigator considers the subject unlikely to comply with study procedures, restrictions and requirements.

9.6 Restrictions during the study

The subjects must be willing to comply to the following restrictions during the entire study duration *i.e.*, from screening to the end-of-study visit.

9.6.1 **General restrictions**

- Subjects shall abstain from snus and all other nicotine containing products from 10 pm the evening prior to the anticipated start of each IP use on Days 1 to 5.
- Subjects shall abstain from smoking the last 24 hours before Day 1 (from approximately 8.00 am on Day -1) until the end of Visit 2 (on Day 5).
- Use of other nicotine-containing products, than defined by this study protocol, is not allowed during the study from Day-1 until the end of Visit 2.
- Subjects are not allowed to eat or drink or conduct any other mouth related procedure (e.g. tooth brushing) 30 minutes before IP use, during IP use and 30 minutes after the IP have been taken out.
- Meals and Dietary Restrictions:

Meals will be served while the study subjects are in the research clinic. Breakfast will be served approximately 1 hour prior to IP use. Lunch will be served 4 hours after start of each IP use. Snack, dinner and evening snack will be served approximately 7, 9 and 11 hours post-IP use, respectively. Water is allowed ad libitum at the clinic except 30 minutes before IP use until one hour after IP use on Days 1-5.

- Alcohol: Consumption of alcohol is not allowed within 48 hours prior to the screening visit or Visit 2. Consumption of alcohol is not allowed during the subject's stay at the clinic during Visit 2.
- Drugs of abuse: Use of drugs of abuse is not allowed during the study (from the screening visit to the end-of-study visit). In addition to the urine drug testing described in Table 8.1-1, additional random testing can be performed at the clinic visits.
- Coffee: Consumption of up to 5 cups of coffee per day will be allowed during the study (*i.e.*, admission to the clinic on Day -1 to the end of Visit 2).
- Xanthine or taurine containing products/beverages: Energy drinks (e.g. Red bull) are not allowed during the study from admission to the clinic on Day -1 until the end of Visit 2.
- Exercise: The subjects must refrain from strenuous exercise (defined as greater than 70% of the maximal pulse rate for one hour or more) during Visit 2.
- Blood donation: The subjects must not donate blood or plasma during the study until three months after the final medical examination at Visit 2.
- Participation in other clinical studies: Study subjects are not allowed to participate in any other interventional clinical study during the study period.

9.6.2 **Prior and concomitant therapy**

Medications (prescribed or non-prescribed medication including antacids, analgesics, herbal remedies, vitamin supplements and minerals) considered necessary for the subject's safety and wellbeing may be given at the discretion of the Investigator during the residential period. Following consultation with the Sponsor, the Investigator will determine whether or not the subject should continue in the study.

9.7 Screen failures

Screen failures are defined as subjects who consent to participate in the clinical study but do not fulfil all eligibility criteria and are not subsequently randomised in the study. A minimal set of screen failure information is required to ensure transparent reporting of screen failure subjects. Minimal information includes documentation of signed and dated informed consent form (ICF) and reason(s) for screening failure.

Subjects who do not meet the criteria for participation in this study may be rescreened.

Re-screening can be performed if any of the following were reasons for screening failure or non-randomisation (as judged by the Investigator):

- Practical reasons.
- Non-significant medical conditions (e.g. influenza, nasopharyngitis).
- Reserve subject in a previous group
- Plasma or blood donation outside allowed time windows.

For subjects who are re-screened, a new screening number will be assigned and a new, signed ICF will be collected.

9.8 Subject withdrawal

9.8.1 *General withdrawal criteria*

Subjects are free to discontinue their participation in the study at any time and for whatever reason without affecting their right to an appropriate follow-up investigation or their future care. If possible, the reason for withdrawal of consent should be documented.

Subjects may be discontinued from the study at any time at the discretion of the Investigator.

Reasons for discontinuation include:

- Subject decision
- Severe non-compliance to study protocol procedures, as judged by the Investigator and/or Sponsor
- Subject is lost to follow-up.
- Significant AEs posing a risk for the subject, as judged by the Investigator and/or Sponsor
- Withdrawal of informed consent to the use of biological samples
- Pregnancy
- Death
- Meeting of an exclusion criterion during the study, which, in the opinion of the Investigator, may pose a risk for the subject

9.8.2 *Procedures for discontinuation of a subject from the study*

A subject who prematurely discontinues participation in the study will always be asked about the reason(s) for discontinuation and the presence of any AEs. If a subject withdraws consent, the Investigator must ask the subject if he/she is willing, as soon as possible, to be assessed according to the procedures scheduled for the end-of-study visit. Any ongoing AEs will be followed as described in Section 11.4.6.12.

The primary reason for discontinuation/early withdrawal must be specified in the eCRF and final product accountability must be performed.

9.8.3 *Subject replacement*

Subjects who are prematurely withdrawn from the study for any reason may not be replaced during the course of the study.

9.9 Randomisation

On Day 1, subjects will be randomised to one of 5 treatment sequences. The five different products are:

- A: ZoneX #2, OND, white tobacco-free nicotine pouch, 5.8 mg nicotine/pouch
- B: ZoneX #3, OND, white tobacco-free nicotine pouch, 10.1 mg nicotine/pouch
- C: Skruf snus fresh slim white, 10.9 mg nicotine/pouch
- D: [REDACTED]
- E: Marlboro Gold, conventional cigarette, 0.8 mg nicotine/cigarette

The 5 randomisation sequences are:

Sequence 1: A:B:C:D:E

Sequence 2: B:C:D:E:A

Sequence 3: C:D:E:A:B

Sequence 4: D:E:A:B:C

Sequence 5: E:A:B:C:D

A computer-generated randomisation list will be created by CTC using SAS Proc Plan, SAS Version 9.4. The randomisation list will contain subject number, sequence and treatment and will be kept by the randomiser until database lock. A copy of the randomisation list will be provided to the research clinic.

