In the morning of Day 1, after pre-use assessments and confirmation of eligibility, the subjects will be randomised and then administered a single pouch/single cigarette of the IP in the sequence to which they have been randomised. Oral nicotine IP will be used for 20 minutes with standard use instructions. The cigarette will be smoked in approximately 5 minutes with puffs taken at regular intervals approximately 30 seconds apart. PK sampling will be done pre-IP use and at 2, 5, 7, 15, 20, 30, 45, 60, 90 minutes, 2, 4, 6 and 8 hours post-IP use start. Sampling for plasma cotinine levels will be taken pre-IP use and at 4, 8 and 12 hours post-IP use start. Used pouches will be collected for analysis of nicotine extraction. Questionnaires will be administered to the subject at defined intervals throughout the day. Safety will be followed throughout the day. Subjects will be allowed to use the IP, to which they are assigned that day, *ad lib* after the 8-hour timepoint until 10 pm.

In the morning of Day 2, after pre-IP use assessments, the subjects will be administered a single pouch/single cigarette of the IP in the sequence to which they have been randomised. IP will be used for 20 minutes with standard use instructions. The cigarette will be smoked in approximately 5 minutes with puffs taken at regular intervals approximately 30 seconds apart. PK sampling will be done pre-IP use and at 2, 5, 7, 15, 20, 30, 45, 60, 90 minutes, 2, 4, 6 and 8 hours post-IP use start. Sampling for plasma cotinine levels will be taken pre-IP use and at 4, 8 and 12 hours post-IP use start. Used pouches will be collected for analysis of nicotine extraction. Questionnaires will be administered to the subject at defined intervals throughout the day. Safety will be followed throughout the day. Subjects will be allowed to use the IP, to which they are assigned that day, *ad lib* after the 8-hour timepoint until 10 pm.

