Baseline symptoms ⁵	11.2.12	X	X	X					
Adverse events ⁶	11.4.6				----- X -----				
Prior and concomitant medications	11.2.7				----- X -----				

BMI = Body mass index, WOCBP = women of childbearing potential, HIV = human immunodeficiency virus

1. Confirmation of eligibility criteria on Day-1 or Day 1

2. WOCBP only. Urine dipstick.

3. Clinical laboratory panel to include testing for SARS-CoV-2 (qPCR testing) on Day 5.

4. Meals (breakfast, lunch, snack, dinner and evening snack) will be served at the research clinic during Visit 2. On Day 1-5, lunch, snack, dinner and evening snack will be served approximately 4, 7, 9 and 11 hours, respectively, after start of each IP use. Breakfast will be served approximately 1 hour before start of each IP use.

5. Baseline symptoms will be recorded up until start of first use of IP on Day 1.

6. Adverse event will be recorded from start of first use of IP on Day 1.

Table 8.1-2 Detailed schedule of events for Day 1, Day 2, Day 3, Day 4 and Day 5

Assessment /time-point	Pre-IP use	Day 1, Day 2, Day 3, Day 4 and Day 5														
		00:00	00:02	00:05	00:07	00:15	00:20	00:30	00:45	01:00	01:30	02:00	04:00	06:00	08:00	12:00
Inclusion/exclusion criteria	X ¹															
Vital signs (Blood pressure and pulse)	X														X	
12-lead ECG															X ²	
Clinical laboratory profile															X ²	
PES	X ³		X ³		X ³											
MCEQ ⁴															X	
PPS															X ²	
Randomisation	X															
IP use		----- X -----													Ad lib use until 10 pm ⁵	
PK blood sampling ⁶	X	X	X	X	X	X	X	X	X	X	X	X	X	X	X	
Cotinine sampling	X												X		X	X ⁷
Nicotine pouch collection								X								
Meals ⁸		----- X -----														
Baseline symptoms ⁹	X															
Adverse events ¹⁰		----- X -----														
Prior and con meds		----- X -----														

1. Confirmation of eligibility criteria on Day-1 or Day 1.
2. Day 5 only. Clinical laboratory panel to include testing for SARS-CoV-2 on Day 5.
3. PES question 1a-g pre-use only, PES question 2a-j at timepoints 2 minutes to 4 hours, PES question 3a-y at timepoint 8 hours, PES question 4a at timepoints 30 min and 8 hours.
4. Cigarette arm only.
5. The number of units of IP used during *ad lib* use will be reported in the eCRF at the end of each treatment day.
6. PK sampling for 8 hours post-IP use on Days 1-5, respectively. Pre-use sample to be taken within 5 minutes of start of IP-use. PK sampling time windows, refer to Section 11.3.1.

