7. No sample to be taken at 12 hours on Day 5.
8. Meals (breakfast, lunch, snack, dinner and evening snack) will be served at the research clinic during Visit 2. Lunch, snack, dinner and evening snack will be served approximately 4, 7, 9 and 11 hours, respectively, after start of each IP use. Breakfast will be served approximately 1 hour before start of each IP use.
9. Baseline symptoms will be recorded up until start of first use of IP on Day 1.
10. Adverse event will be recorded from start of first use of IP on Day 1.

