17.6 Analysis of secondary endpoints

17.6.1 *Pharmacokinetics*

Refer to section 17.5.1.

17.6.2 *In vivo extracted amount of nicotine*

The data needed for the analysis of in vivo extracted amount of nicotine are the individual data of amount of nicotine for unused reference pouches and the amount of nicotine left in the study pouches. The mean nicotine concentration of the reference pouch and weight of each individual study pouch and residual nicotine amount will be used to calculate the extracted amount. The mean of extracted amount (mg/unit) and extraction fraction (%) of nicotine for each IP pouch, will be calculated. The extracted dose of nicotine will be analysed using the signed Wilcoxon rank sum test for within subject difference (i.e. between IPs). Amount of

nicotine in reference pouches and in used pouches will be presented through descriptive statistics.

17.6.3 *Products evaluation scale*

Each sub-question, sub-category and the total score of Questions 1a-g (sub-category 1), 2a-j (sub-category 2), 3a-y (sub-category 3) and 4a will be presented using descriptive statistics at selected timepoints by product including a graph of the mean at each time point.

The total score of PES and the sub-categories will be calculated for each product and intraindividual difference for each timepoint assessed will be analysed using a Wilcoxon Signed Rank Sum test.

17.6.4 *Modified cigarette evaluation questionnaire*

Frequency (number and percentage) for each sub-question will be presented using tables.

17.6.5 *Products preference scale*

The sub-questions 1 will be presented using a frequency table with number of observations and all combinations of the subject's preference.

The sub-question 2 will be presented using a frequency table with number of observations and percent.

No statistical testing will be performed on sub-questions.

17.6.6 *Adverse events*

An overview of all AEs, including SAEs, intensity, relationship to IP, and deaths will be presented by SOC and PT.

Incidence of AEs and SAEs will be summarised by SOC and PT by sequence and overall.

All AE data will be listed by subject and include the verbatim term entered by the Investigator.

17.6.7 *Clinical laboratory analyses*

Clinical laboratory data will be summarised overall with absolute and percent change from baseline.

Abnormal, clinically significant values will be summarised separately, if considered appropriate.

All data will be listed by subject.

17.6.8 *Vital signs*

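### The five sequences are cyclic shifts of one order, so from Day 2 each product always follows the same product; secondary cotinine and pre-use PES comparisons are exposed, primary nicotine largely is not

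*Protocol*

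**What the plan says.** Section 9.9: "On Day 1, subjects will be randomised to one of 5 treatment sequences". Sequence 1 is ABCDE; the next is "Sequence 2: B:C:D:E:A", and each further sequence shifts the order by one more place.

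Under section 8.1 the five products are used on five consecutive days. On Days 1 to 4 the day's product is also used ad lib "after the 8-hour timepoint until 10 pm". Section 9.6.1 requires subjects to "abstain from snus and all other nicotine containing products from 10 pm the evening prior", and its wording on smoking abstinence implies a start near 8 am, so about 10 hours separate the end of ad lib use from the next product.

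Section 17.5.1 calculates nicotine C_max and AUC_t with and without baseline correction. It analyses them with fixed effects for period, sequence and product and a random subject effect, with no carry-over term.

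On cotinine, section 8.1 states: "Sampling for plasma cotinine levels will be taken pre-IP use and at 4, 8 and 12 hours post-IP use start". A note to Table 8.1-2 adds: "No sample to be taken at 12 hours on Day 5". Section 17.6.10 leaves the cotinine analysis to the SAP.

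On the product evaluation scale, the notes to Table 8.1-2 specify "PES question 1a-g pre-use only". Section 17.6.3 calculates the total and sub-category scores for each product and says the "intraindividual difference for each timepoint assessed will be analysed using a Wilcoxon Signed Rank Sum test".

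**The concern.** A cyclic list balances products over days but not over predecessors. The effect of a product is then nearly inseparable from what the product before it left behind. Only Day 1, when the predecessor is the subject's own snus, helps to separate them.

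Two secondary comparisons depend on this. Cotinine is cleared slowly, so a day's level includes a contribution from the previous product unless the analysis uses that day's pre-use sample. PES 1a-g is recorded before the day's product is used. Apart from anticipation in an open-label study, such a score cannot show an effect of using that product. From Day 2, a test of A against B on it is largely a test of the morning after E against the morning after A.

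**Working it through.** The protocol gives no sample size, variance or half-life figure to reproduce. The inputs are the five sequences (9.9), 24 subjects (9.3), the schedule (8.1, 9.6.1) and the model (17.5.1). Half-lives, levels and exposures below are assumptions.

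**1. Predecessor pairs.** The listed sequences contain AB, BC, CD, DE and EA, four times each: 5 of 20 ordered pairs. The ten Williams sequences (ABECD, BCADE, CDBEA, DECAB, EADBC and their reversals) contain all 20, twice each, and remain balanced over days.

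**2. Weight of carry-over in a contrast.** Of 24 subjects, four sequences get 5 and one gets 4. A follows E in every sequence except Sequence 1, where A is first. Its share is therefore 19/24 = 0.79, or 20/24 = 0.83 if Sequence 1 has 4 subjects. The same holds for B after A with Sequence 2. Least squares with subject, period and product effects gives these A-B weights:

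| List | On the carry-over of E | On the carry-over of A |
|---|---|---|
| Cyclic, three of the five splits | +0.79 | -0.79 |
| Cyclic, Sequence 1 has 4 | +0.83 | -0.80 |
| Cyclic, Sequence 2 has 4 | +0.80 | -0.83 |
| Williams, all 210 splits | at most 0.10 in size | 0.16 to 0.26 in size |

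With Williams, B also carries 0.16 to 0.26, and C and D at most 0.10. Carry-over common to all products cancels under either list.

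For pre-use PES, the mean A-B difference without period adjustment has weights of 0.79 to 0.83 on E and on A in the current list. With Williams they are 0.17 to 0.25 on A and B and at most 0.08 elsewhere. The wording of 1a-g is not given, so the size of its carry-over is not estimated.

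**3. Mean variance of the ten contrasts** (units of within-subject variance):

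| | Planned model | Carry-over added | Ratio |
|---|---|---|---|
| Cyclic, Days 1-5 | 0.0835 | 0.532 | 6.4 |
| Williams, Days 1-5 | 0.0835-0.0838 | 0.0885-0.0891 | 1.06-1.07 |
| Cyclic, Days 1-4 (12-hour cotinine) | 0.1114 | 0.5917 | 5.3 |
| Williams, Days 1-4 | 0.1114-0.1119 | 0.1372-0.1382 | 1.23-1.24 |

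**4. Nicotine C_max, unadjusted version only.** Fraction carried in: f = 0.5^(10/half-life). At assumed half-lives of 2, 3 and 4 h, f is 3.1%, 9.9% and 17.7%. With an assumed product C_max of 12 ng/mL, evening levels of 20 and 10 ng/mL for the two predecessors, and no further decay before C_max, the shift is ((12 + 20f)/(12 + 10f))^0.79 - 1 = 2.0%, 6.0% and 10.0%. Little should remain after baseline adjustment.

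**5. Cotinine without pre-use correction.** Model: today's level = today's exposure + 0.5^(24/half-life) x yesterday's level. The factor is 0.33 at 15 h and 0.44 at 20 h. Over 400 random exposure sets, each product uniform on 50-150:

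| | Cyclic | Williams |
|---|---|---|
| Mean absolute bias, ten contrasts | 8.2-10.7 | 3.0-4.4 |
| Worst contrast | 16-22 | 6-9 |
| Mean absolute bias, 12-hour sample, Days 1-4 | 7.7-10.1 | 3.6-5.2 |

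Williams has the smaller bias in 76-81% of set-and-contrast combinations (71-74% for Days 1-4). An example with A = 60 and B = C = D = 100:

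| E | E-A: true | Cyclic | Williams | B-A: true | Cyclic | Williams |
|---|---|---|---|---|---|---|
| 60 | 0 | 10 to 14 | -1.5 to 1.5 | 40 | 35-38 | 34-38 |
| 100 | 40 | 39.5-40.0 | 33.4-36.6 | 40 | 26-30 | 33-37 |
| 140 | 80 | 65-70 | 67-73 | 40 | 16-22 | 31-37 |

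**6. Cotinine corrected for the pre-use level projected forward.** Under the current list the mean absolute bias is 0 with the right half-life and 0.6-1.1 if the half-life is 3 h wrong.

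**The case against.** The main case against is that analysis wording alone can deal with both exposures. Correcting cotinine for the pre-use sample already scheduled leaves the new list little to add there, and one sentence settles the PES point. The cotinine analysis is properly left to the SAP. The protocol never claims carry-over balance, the planned model is as precise under the cyclic list, and the 6.4-fold penalty concerns a term nobody has planned. The cotinine and nicotine sizes rest on assumed inputs, and Williams is worse for some contrasts.

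All of that is true, and it limits the point to a safeguard. It does not remove it. No later analysis can supply the 15 predecessor pairs the list omits, so the assumption of no carry-over cannot usefully be checked. The safeguard costs almost nothing if adopted in time.

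It is also fair that open-label anticipation can move a pre-use rating, and that 17.6.3 does not say between products in so many words. But it calculates the scores for each product before testing within-subject differences, so comparing products is the natural reading. Anticipation is not an effect of having used the product.

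**Conclusion.** The concern holds. Carry-over left uncorrected shifts a product contrast by about 0.8 times the difference between two fixed predecessors' carry-over. That follows from the listed sequences and 24 subjects alone. How large the carry-over is rests on assumed half-lives and exposures.

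Primary nicotine is largely protected. The reservation is that section 17.5.1 adjusts only when possible, also calculates unadjusted values, and does not say which version carries the primary comparison. Cotinine is exposed only if the pre-use sample goes unused; the deferral to the SAP is not faulted. The planned PES test of questions 1a-g needs correcting under either list. This should be fixed as an inexpensive improvement to secondary comparisons; it does not invalidate the primary result.

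**What to change.** **Before randomisation:** replace the list in 9.9 with the ten Williams sequences given above, 2 or 3 of the 24 subjects on each, and add first-order carry-over as a sensitivity term.

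**If the current list is already in use:** name baseline-adjusted C_max and AUC_t as the primary version, and correct each day's cotinine for that day's measured pre-use level projected forward.

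**In either case:** state in 17.6.3 that PES sub-category 1 is that day's baseline and is not tested as a product outcome.

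**Cost:** a new randomisation list, one protocol paragraph and one sentence in 17.6.3, with the same subjects, days and samples. The clinic handles ten orders instead of five. Because 24 is not a multiple of 10, contrast variance under the planned model rises by 0 to 0.4%. Williams reduces unfitted carry-over bias on average but does not remove it, and a few contrasts can be worse.
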